3.5.2.2 Other medication restrictions

- (a) Use of immunosuppressive medication (other than prior stable oral corticosteroids for the maintenance treatment of asthma or bolus systemic steroids for the treatment of an asthma exacerbation) or administration of live/attenuated vaccines is not allowed. Topical administration of immunosuppressive medication and local corticosteroid injections may be allowed at the discretion of the Investigator after discussion with the AstraZeneca Study Physician.
- (b) Patient should not receive an allergen immunotherapy injection on the same day as IP administration

- (c) Patients who are on theophylline or digoxin; the Investigator should ensure the levels of each of these medications does not exceed the upper limit of therapeutic range. The Investigator will also be responsible for ensuring that these levels are regularly checked, assessed, and documented as per local practice
- (d) Patients should not take any other excluded medications:
 - Five-lipoxygenase inhibitors (eg, Zileuton)
 - Oral or ophthalmic non-selective β -adrenergic antagonist (eg, propranolol)

A table with medication-related restrictions is presented in [Appendix F](#).

3.5.2.3 Other restrictions

- (a) Fertile and sexually active patients or their partners should use effective contraceptive methods throughout the study and for at least for 16 weeks (5 half-lives) after last administration of the IP. Male patients should refrain from fathering a child or donating sperm from the time of informed consent and for 16 weeks (5 half-lives) after last dose of IP (see Section 3.1, inclusion criteria 3, 4 and 5; Section 7.3).
- (b) Patients must abstain from donating blood and/or plasma from the time of informed consent and for 16 weeks (5 half-lives) after last dose of IP.

3.6 Discontinuation from investigational product

Patients will be discontinued from IP in the following situations:

1. Patient decision. The patient is at any time free to discontinue treatment without prejudice to further treatment (see Section 3.7)
2. Adverse event (AE) that in the opinion of the Investigator contraindicates further dosing
3. Risk to patient as judged by the Investigator or AstraZeneca
4. Severe non-compliance to study protocol
5. Eligibility requirement found not to be fulfilled (see Section 3.4)
6. Pregnancy
7. Lost to follow-up³
8. Development of any study specific criteria for discontinuation:
 - (a) Anaphylactic reaction to the IP requiring administration of epinephrine
 - (b) Development of helminth parasitic infestation requiring hospitalization
 - (c) If 2 consecutive doses of IP missed or more than 2 scheduled doses of IP are missed during course of the study

³ Patient is considered lost to follow up when any of the following attempts of contact are failed: -3 attempts of either phone calls, faxes, or emails; - having sent 1 registered letter/certified mail; 1 unsuccessful effort to check the vital status of the patient using publicly available sources, if allowed by local regulations.

(d) An asthma-related event requiring mechanical ventilation

All patients who prematurely discontinue IP should return to the study center and complete the procedures described for the Premature Investigational Product Discontinuation Visit (IPD) within 4 weeks \pm 7 days after the last dose of IP and for the final Follow-up visit at 16 weeks (\pm 7 days) after the last dose of IP (see [Table 1](#) and [Table 2](#)).

Reasons for premature discontinuation of IP should be recorded in the eCRF.

3.7 Withdrawal from the study

3.7.1 Withdrawal of Informed Consent

Patients are free to withdraw from the study at any time (IP and assessments) without prejudice to further treatment. Patients who discontinue IP will be discontinued from the study.

A patient who withdraws consent will always be asked about the reason(s) and the presence of any adverse events (AE). The Investigator will follow up AEs outside of the clinical study. The enrolment/randomization code of the withdrawn patient cannot be reused.

If patient agrees, he/she will be asked to return to the study center and complete procedures described for the IPD and FU visits within 4 weeks (+7 days) and 16 weeks (\pm 7 days) after the last dose of IP, respectively.

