2. STUDY OBJECTIVES

(a) Primary Objective

Objective	Endpoint

 1. To assess the safety and tolerability of 2 dosing regimens of benralizumab for adult patients during the 56-week treatment period and through the follow-up period (16 weeks from day of last dose) 2. To assess the safety and tolerability of 2 dosing regimens of benralizumab for adolescent patients during the 108-week treatment period and through the follow-up period (16 weeks from day of last dose) 	
 • Number of AEs/SAEs • Laboratory variables • Physical examination

(b) Secondary Objectives

Objective	Endpoint

 1. To evaluate the effect of 2 dosing regimens of benralizumab on asthma exacerbations in adult patients during the 56-week treatment period and through the follow-up period (16 weeks from day of last dose) 2. To evaluate the effect of 2 dosing regimens of benralizumab on asthma exacerbations in adolescent patients during the 108-week treatment period and through the follow-up period (16 weeks from day of last dose) 	
 • Annual asthma exacerbation rate, where an asthma exacerbation is defined by a worsening of asthma requiring the use of systemic corticosteroids for at least 3 days, and/or an in-patient hospitalization, and/or an emergency department or urgent care visit.

 1. To evaluate the effect of two dosing regimens of benralizumab on health care utilization and work and productivity loss for adult patients during the 56-week treatment period and through the follow-up period (16 weeks from day of last dose) 2. To evaluate the effect of two dosing regimens of benralizumab on health care utilization and work and productivity loss for adolescent patients during the 108-week treatment period and through the follow-up period (16 weeks from day of last dose) 	
 • WPAI+CIQ • Hospitalizations, ED visits, urgent care visits and all other outpatient visits due to asthma

Objective	Endpoint

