4.2.3.4 Randomized treatment period assessments

For Visits 2 -16 (Visit 2 - 29 for adolescents), spirometry and blood sampling (for hematology, serum chemistry, PK, ADA/nAb) may be performed 1 day prior to the scheduled date of IP injection, at the discretion of the investigator. All other study procedures must be done on the scheduled day of IP injection. Urine pregnancy tests must be done prior to IP administration. The patient will receive 56 weeks treatment (108 weeks for adolescents), with the last dose of benralizumab administered at Visit 14 (Visit 27 for adolescents). Adolescent patients in EU will be administered IP according to open-label schedule.

Patients will have scheduled visits at 4-week intervals to complete protocol-specific assessments and IP administration, as listed in [Table 1](#) and [Table 2](#); Restrictions as set out in [Section 3.5.2](#) will continue to apply throughout the treatment period. In case of an asthma worsening/exacerbation (see [Section 5.1.1](#)), patients should be evaluated at the study center,

when feasible, at an unscheduled visit, or ordinary visit if the worsening happens to fall within a scheduled visit window.

Patients' lung function will be monitored at the site, as well as responses to questionnaires (see Section 5.3.2 for details).

At Week 56 (Week 108 for adolescents) patients will come to the center for the End of Treatment (EOT) visit.

Patients who prematurely discontinue IP (see Section 3.6) should return to the study center and complete procedures described for the IPD and Follow-up visits within 4 weeks (± 7 days) and 16 weeks (± 7 days) after the last dose of IP, respectively.

Completion or early termination of the treatment will be registered via IWRS/IVRS for each patient.

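### Protocol 3.7.1 removes from the study every patient who stops IP, which conflicts with the 16-week follow-up in 3.6 and 4.2.3.4 and with the primary objective

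*Protocol*

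**What the plan says.** Three protocol sections deal with a patient who stops IP early.

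- **Section 3.6** lists the reasons for stopping (patient decision, adverse event, pregnancy, anaphylaxis, helminth infestation, missed doses and others). It then says: "All patients who prematurely discontinue IP should return to the study center", both for IPD and "for the final Follow-up visit at 16 weeks" after the last dose.
- **Section 4.2.3.4** repeats the rule: "Patients who prematurely discontinue IP (see Section 3.6) should return to the study center and complete procedures described for the IPD and Follow-up visits".
- **Section 3.7.1**, headed as withdrawal of informed consent, says: "Patients who discontinue IP will be discontinued from the study". Turning to a patient who withdraws consent, it says: "The Investigator will follow up AEs outside of the clinical study". It closes: "If patient agrees, he/she will be asked to return to the study center and complete procedures described for the IPD and FU visits".

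The primary objective in Section 2 covers safety and tolerability during treatment and through follow-up, with follow-up defined as 16 weeks from the last dose. Section 3.5.2.3 equates 16 weeks with 5 half-lives.

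The IPD visit is timed in three ways. Sections 3.6 and 4.2.3.4 give 4 weeks ±7 days after the last dose. Section 3.7.1 gives 4 weeks +7 days after the last dose. Footnote j of Table 1 (footnote i of Tables 2A and 2B) gives 4 weeks +7 days counted from the last scheduled site visit.

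**The concern.** Stopping IP and leaving the study are different events, and the sentence in 3.7.1 merges them. It is unqualified and worded as mandatory, whereas the return visits in 3.6 and 4.2.3.4 are worded as recommendations.

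A site has a direct route to that sentence. The first stopping reason in 3.6, patient decision, points to Section 3.7, whose only subsection is 3.7.1. A patient who simply wants no more injections, perhaps because of an adverse event, is therefore referred to text that ends study participation and makes the IPD and follow-up visits depend on agreement. Two nearby sections do not settle the matter: 4.3 describes the final follow-up visit only for patients who complete the end-of-treatment visit, and 7.1.3.1 ends AE collection at Week 68 or Week 120 without a rule for patients who stop IP early.

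The SAP (4.2.5.1) reports the number and percentage of patients with at least one AE, separately for the on-treatment, post-treatment and on-study periods. A patient closed early stays in the full analysis set but is observed for less time, so the on-study and post-treatment percentages can stay the same or fall, never rise. Patients who stopped because of an AE are among those affected.

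**Working it through.** **1. The plan's own follow-up length.** Adults: last dose Week 52, follow-up Week 68, so 68 − 52 = 16 weeks. Adolescents: 120 − 104 = 16 weeks. The scheduled study days in SAP Appendix A, Table 2 agree: 477 − 365 = 112 days and 841 − 729 = 112 days. The 16 weeks reproduce exactly in both age groups.

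**2. What one patient would lose if 3.7.1 were applied literally.** Days lost = 112 − day of exit after the last dose.

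| Exit | Day | Days lost | Share of 112 |
|---|---|---|---|
| At IPD, early edge of ±7 days | 21 | 91 | 81% |
| At IPD, nominal | 28 | 84 | 75% |
| At IPD, late edge | 35 | 77 | 69% |
| At last dose | 0 | 112 | 100% |

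If 3.6 and 4.2.3.4 are followed, nothing is lost: the follow-up visit falls on day 112 (105 to 119 with its window).

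**3. Across the study.** The documents give no rate of IP discontinuation. Assume 5%, 10% or 15% of 1200 patients (the minimum in Section 8.2), with every one of them leaving at the stated point. Patient-years lost = patients × 12/52 for exit at IPD, or × 16/52 for exit at last dose.

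| Assumed rate | Patients | Exit at IPD | Exit at last dose | Post-IPD time, if stoppers are followed |
|---|---|---|---|---|
| 5% | 60 | 13.8 | 18.5 | 13.8 |
| 10% | 120 | 27.7 | 36.9 | 27.7 |
| 15% | 180 | 41.5 | 55.4 | 41.5 |

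With a year of 365.25 days, exit at IPD gives 13.8, 27.6 and 41.4. For scale, the completers would contribute 1200 × 95%, 90% or 85% × 12/52 = 263, 249 or 235 patient-years after the end-of-treatment visit. Planned adult on-study time is about 1200 × 68/52 = 1569 patient-years, so the exit-at-IPD loss is 13.8/1569 to 41.5/1569, about 1% to 3% of it.

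**4. What the rest of the plan assumes.**

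- Protocol 1.5: patients who do not move to MELTEMI may remain until IPD or end of treatment, and then follow-up.
- Protocol 7.1.3.3: each AE record holds the action taken with IP separately from withdrawal from the study.
- SAP 3.1.1: a post-treatment AE period follows the IPD visit, with a rule for patients who attend only the follow-up visit.
- SAP 4.1: data are used even when treatment stopped early, unless consent is withdrawn.
- SAP 4.2.1: completion of treatment and discontinuation from the study are tabulated separately.

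All five fit the rule in 3.6. None fits a literal reading of the sentence in 3.7.1.

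**The case against.** The best answer is that the passages can be read together: a patient who stops IP leaves the 4-weekly schedule, completes IPD and follow-up, and then exits. On that reading the full 16 weeks are kept. Section 3.6 places its return rule straight after the list of stopping reasons, so patients stopped for an AE are covered explicitly. Section 3.7.1 itself asks for the IPD and follow-up visits. Section 7.3.1 follows pregnancy outcomes even after a patient has left the study. The AE that caused the stop is still reported as a discontinuation AE. This is a fair account of the likely intention, and it stands as such. It does not remove the conflict, because 3.7.1 does not say it.

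A reader might go further and infer any of the following. The documents do not support them.

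- **That safety follow-up is planned to end early.** Sections 1.5, 3.6 and 4.2.3.4 and the SAP all point the other way.
- **That the loss falls on exactly the patients who were harmed.** The sentence covers every reason for stopping, including patient decision, non-compliance and missed doses.
- **That AEs are followed outside the study for everyone who stops IP.** That sentence follows one about a patient who withdraws consent, under a heading on consent withdrawal. The conditional visit wording is most naturally read the same way, and for those patients some conditionality is unavoidable.
- **That the primary safety result is biased.** The direction is clear if sites act on 3.7.1, but nothing shows that they would, and the size rests on an assumed rate.

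**Conclusion.** The contradiction is real and bears on the window named in the primary objective. It is a wording conflict that creates a risk if 3.7.1 is read literally. For a patient who leaves at IPD, about 84 of 112 post-dose days would go unobserved (77 to 91 with the visit window).

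For the study, about 14 to 42 patient-years is a ceiling for exit at IPD. It assumes that 5% to 15% of 1200 patients stop IP and that every site ignores 3.6 and 4.2.3.4. It also counts patients lost to follow-up or withdrawing consent, whose time no rewording recovers. In the other direction, 1200 is a minimum: the synopsis gives 2133 enrolled, and the sentence applies to adolescents as well.

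**What to change.** Reconcile 3.7.1 with 3.6, 4.2.3.4 and the primary objective, so that the protocol gives one answer to whether stopping IP alone, without withdrawing consent, ends AE and SAE collection in the study. Check the cross-reference from the patient-decision reason in 3.6 against that answer. Make clear in 3.7.1 that the out-of-study AE follow-up and the visits conditional on agreement concern patients who withdraw consent.

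In the same edit, reconcile the IPD timing: the window (±7 days in 3.6 and 4.2.3.4, +7 days in 3.7.1 and the table footnotes) and the anchor (last dose in those sections, last scheduled site visit in the footnotes). This matters for the analysis because SAP 3.1.1 closes the on-treatment period at the IPD visit for patients who stop early.

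The cost is a protocol clarification and a note to sites. The visits are already in the schedule. The SAP period definitions need no change if the reconciled text keeps the visits they refer to, and the plan already records stopping IP and leaving the study separately.

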3.8 Withdrawal of informed consent for donated biological samples

If a patient withdraws consent to the use of donated biological samples, the samples will be disposed of/destroyed and the action documented. If samples are already analyzed, AstraZeneca is not obliged to destroy the results of this research.

As collection of the biological samples is an integral part of the study, then the patient is withdrawn from further study participation.

If the patient only withdraws consent for the retention of samples for future exploratory use, the patient will not be withdrawn from the study.

The Principal Investigator or designee:

- Ensures patients' withdrawal of informed consent for the use of donated samples is notified immediately to AstraZeneca
- Ensures that biological samples from that patient, if stored at the study center, are immediately identified, disposed of /destroyed, and the action documented
- Ensures the local laboratory(ies) holding the samples is/are informed about the withdrawn consent immediately and that samples are disposed/destroyed
- Ensures that the patient and AstraZeneca are informed about the sample disposal.

Revised Clinical Study Protocol
Drug Substance Benralizumab (MEDI-563)
Study Code D3250C00021
Edition 4.0
Date 13 January 2016

AstraZeneca ensures the central laboratory(ies) holding the samples is/are informed about the withdrawn consent immediately and that samples are disposed of/destroyed and the action documented.

4. STUDY PLAN AND PROCEDURES

Table 1 Study Assessments Schedule – Adults

Assessment/ activity	Refer to	Treatment																	EOT ^m	IPD ^j	FU	UNs ⁱ		
		V1	V2	V3	V4	V5	V6	V7	V8	V9	V10	V11	V12	V13	V14	±3	±3	±3					±7	±7
		w0	w4	w8	w12	w16	w20	w24	w28	w32	w36	w40	w44	w48	w52									
Visit window (days) ^c																								
		±0	±2	±3	±3	±3	±3	±3	±3	±3	±3	±3	±3	±3	±3	±3	±3	±7	±7	±7	N/A			
Inclusion/exclusion criteria	3.1/3.2	X																						
Informed consent	10.4	X																						
Medical and asthma history	5.2.1	X ^a																						
Comprehensive CV history ^k	5.2.1	X																						
Height	5.3.1	X ^b					X											X						
FSH ^g	5.2.5.1	X																						
Complete physical examination	5.2.2.1	X ^b																X						
Brief physical examination	5.2.2.2		X	X	X	X	X	X	X	X	X	X	X	X	X	X	X					X		
Weight	5.3.1	X ^b					X											X						
Vital Signs	5.2.3	X ^b	X	X	X	X	X	X	X	X	X	X	X	X	X	X	X	X	X	X	X	X		
Local ECG	5.2.4	X ^b					X											X						
Serum chemistry ^d	5.2.5	X ^b			X		X					X						X						
Hematology	5.2.5	X ^b			X		X					X						X				X		

Table 1 Study Assessments Schedule – Adults

Assessment/ activity	Refer to	Treatment																	EOT _m	IPD _j	FU	UNS ⁱ	
		V1	V2	V3	V4	V5	V6	V7	V8	V9	V10	V11	V12	V13	V14	V15	V16						
		w0	w4	w8	w12	w16	w20	w24	w28	w32	w36	w40	w44	w48	w52	w56	w68						
		±0	±2	±3	±3	±3	±3	±3	±3	±3	±3	±3	±3	±3	±3	±3	±3	±3	±7	±7	±7	±7	N/A
Urinalysis	5.2.5	X ^b		X				X											X				
Urine pregnancy test (dipstick) ^e	5.2.5.1	X ^b	X	X	X	X	X	X	X	X	X	X	X	X	X	X	X	X	X	X	X	X	X
PK ^f	5.3.6	X ^b		X				X											X				
ADA/nAb ^f	5.3.7.1	X ^b		X				X											X				
ACQ-6	5.3.2.1	X ^b								X									X				
AQLQ(S)+I2	5.3.2.2	X ^b								X									X				
WPAI+CIQ	5.3.2.3	X ^b								X													
EQ-5D-5L	5.3.2.4	X ^b	X	X	X	X	X	X	X	X	X	X	X	X	X	X	X	X	X	X	X	X	X
Health care resource utilization	5.3.3	X ^b	X	X	X	X	X	X	X	X	X	X	X	X	X	X	X	X	X	X	X	X	X
Assessment of asthma exacerbations	5.1.1	X ^b	X	X	X	X	X	X	X	X	X	X	X	X	X	X	X	X	X	X	X	X	X
Pre- BD spirometry ^l	5.1.2	X ^b								X									X				X
Post- BD spirometry ^l	5.1.2	X ^b																	X				X
Randomization (where applicable)	6.5	X																					
Administration of IP ^h	6.8	X	X	X	X	X	X	X	X	X	X	X	X	X	X	X	X	X	X	X	X	X	X
Adverse events	7	X ^a	X	X	X	X	X	X	X	X	X	X	X	X	X	X	X	X	X	X	X	X	X
Concomitant medication	3.5	X ^a	X	X	X	X	X	X	X	X	X	X	X	X	X	X	X	X	X	X	X	X	X

- a Medical and asthma history, AEs and concomitant medications will be linked to the predecessor study to create a complete and continuous record for the patient.
 - b Assessments done at the EOT visit of the predecessor study do not need to be repeated at Visit 1 of this study, as the data will be duplicated between study databases (see Section 4.1.1).
 - c All visits are to be scheduled from the date of randomization but not from the date of previous visit
 - d Detailed schedule for serum chemistry tests provided in Section 5.2.5, Table 3 and Table 4
 - e For WOCBP, urine HCG test to be done at center on each treatment visit before IP administration.
 - f PK, ADA and nAb samples to be collected before IP administration.
 - g FSH test done only for female patients <50 years who have been amenorrheic for >12 months to confirm postmenopausal status
 - h In case of anaphylaxis additional samples to be taken (see Section 6.9)
 - i Unscheduled visits may be initiated as needed, and additional assessments performed at these visits, at the discretion of the Investigator
 - j IPD visit should be completed within 4 weeks (+7 days) after last scheduled site visit
 - k Refer to CRF for specific CV history to be collected
 - l All patients transitioning from ZONDA into this study are exempt from performing the post-BD assessments. The pre-BD measurement from EOT for ZONDA patients will serve as the first pre-BD measurement for these patients in BORA.
 - m Patients transitioning into Study D3250C00037 will complete EOT assessments for this study at the same visit during which they transition. Patients who are asked to transition into this study by the Investigator must do so at the next odd-numbered visit (ie, Visit 5, 7, 9, or 11) once the study has started at their site (see Section 4.2).
- D Days; EOT End-of-treatment; FU Follow-up; R Randomization; V Visit; UNS Unscheduled; W Week; IPD Premature IP Discontinuation

Table 2A Study Assessments Schedule – Adolescents: Weeks 0 to 64

Assessment/ activity	Refer to	Treatment																IPD _i	UNS _h	
		Visit window (days) ^c																		
		V1 w0	V2 w4	V3 w8	V4 w12	V5 w16	V6 w20	V7 w24	V8 w28	V9 w32	V10 w36	V11 w40	V12 w44	V13 w48	V14 w52	V15 w56	V16 w60			V17 w64
		±0	±2	±3	±3	±3	±3	±3	±3	±3	±3	±3	±3	±3	±3	±3	±7	±7	N/A	
Inclusion/exclusion criteria	3.1/3.2	X																		
Informed consent+assent	10.4	X																		
Medical and asthma history	5.2.1	X ^a																		
Height	5.3.1	X ^b					X					X							X	
Complete physical examination	5.2.2.1	X ^b					X						X						X	
Brief physical examination	5.2.2.2		X		X	X		X	X	X	X	X		X	X	X	X			X
TBnk Flow Cytometry	5.3.5	X ^b			X			X					X		X				X	
Immunological Assessments	5.3.4.1	X ^b			X			X					X		X				X	
Weight	5.3.1	X ^b						X					X						X	
Vital Signs	5.2.3	X ^b	X	X	X	X	X	X	X	X	X	X	X	X	X	X	X	X	X	X
Local ECG	5.2.4	X ^b						X							X				X	X
Serum chemistry ^d	5.2.5	X ^b			X			X							X				X	
Hematology	5.2.5	X ^b			X			X							X				X	
Urinalysis	5.2.5	X ^b			X			X							X				X	
Urine pregnancy	5.2.5.1	X ^b	X	X	X	X	X	X	X	X	X	X	X	X	X	X	X	X	X	X

Table 2A Study Assessments Schedule – Adolescents: Weeks 0 to 64

Assessment/ activity	Refer to	Treatment																IPD i	UNS h	
		Visit window (days) ^c																		
		V1 w0	V2 w4	V3 w8	V4 w12	V5 w16	V6 w20	V7 w24	V8 w28	V9 w32	V10 w36	V11 w40	V12 w44	V13 w48	V14 w52	V15 w56	V16 w60			V17 w64
test (dipstick) ^e		±0	±2	±3	±3	±3	±3	±3	±3	±3	±3	±3	±3	±3	±3	±3	±7	±7	N/A	
PK ^f	5.3.6	X ^b		X		X		X					X			X			X	
ADA/nAb ^f	5.3.7.1	X ^b		X		X		X					X			X			X	
ACQ-6	5.3.2.1	X ^b			X		X			X				X					X	
AQLQ(S)+I2	5.3.2.2	X ^b			X		X			X				X					X	
WPAI+CIQ	5.3.2.3	X ^b													X				X	
EQ-5D-5L	5.3.2.4	X ^b	X	X	X	X	X	X	X	X	X	X	X	X	X	X	X	X	X	X
Health care resource utilization	5.3.3	X ^b	X	X	X	X	X	X	X	X	X	X	X	X	X	X	X	X	X	X
Assessment of asthma exacerbations	5.1.1	X ^b	X	X	X	X	X	X	X	X	X	X	X	X	X	X	X	X	X	X
Pre- BD spirometry	5.1.2	X ^b				X								X					X	X
Post- BD spirometry	5.1.2	X ^b												X					X	
Randomization	6.5	X																		
Administration of IP ^j	6.8	X	X	X	X	X	X	X	X	X	X	X	X	X	X	X	X	X	X	X
Adverse events	7	X ^a	X	X	X	X	X	X	X	X	X	X	X	X	X	X	X	X	X	X
Concomitant medication	3.5	X ^a	X	X	X	X	X	X	X	X	X	X	X	X	X	X	X	X	X	X

- a** Medical and asthma history, AEs and concomitant medications will be linked to the predecessor study to create a complete and continuous record for the patient.
- b** Assessments done at the EOT visit of the predecessor study do not need to be repeated at Visit 1 of this study, as the data will be duplicated between study databases (see Section 4.1.1).
- c** All visits are to be scheduled from the date of randomization but not from the date of previous visit
- d** Detailed schedule for serum chemistry tests provided in Section 5.2.5, Table 3 and Table 4
- e** For all adolescent females, urine HCG test to be done at center on each treatment visit before IP administration.
- f** PK, ADA and nAb samples to be collected before IP administration.
- g** In case of anaphylaxis additional samples to be taken (see Section 6.9)
- h** Unscheduled visits may be initiated as needed, and additional assessments performed at these visits, at the discretion of the Investigator
- i** IPD visit should be completed within 4 weeks (+7 days) after last scheduled site visit
- j** For adolescent patients in the EU, IP administration is Q4W for the first 3 doses (dummy injection of placebo for those patients on benralizumab in the predecessor studies) and then Q8W thereafter, with no injection of placebo at the 4 week interim visits.

D Days; EOT End-of-treatment; FU Follow-up; R Randomization; V Visit; UNS Unscheduled; W Week; IPD Premature IP Discontinuation

Table 2B Study Assessments Schedule – Adolescents: Weeks 68 to 120

Assessment/ activity	Refer to	Treatment											EOT	IPD ⁱ	FU	UNS ^h	
		V18	V19	V20	V21	V22	V23	V24	V25	V26	V27	V28					
		w68	w72	w76	w80	w84	w88	w92	w96	w100	w104	w108					w120
		±7	±7	±7	±7	±7	±7	±7	±7	±7	±7	±7	±7	±7	±7	±7	N/A
Height	5.3.1		X					X						X	X		
Complete physical examination	5.2.2.1		X					X						X	X		
Brief physical examination	5.2.2.2	X		X	X	X	X	X	X	X	X	X	X			X	X
TBnk Flow Cytometry	5.3.5			X				X						X	X	X	
Immunological Assessments	5.3.4.1			X				X						X	X	X	
Weight	5.3.1		X						X					X	X		
Vital Signs	5.2.3	X	X	X	X	X	X	X	X	X	X	X	X	X	X	X	X

Table 2B Study Assessments Schedule – Adolescents: Weeks 68 to 120

Assessment/ activity	Refer to	Treatment												EOT	IPD ⁱ	FU	UNS ^h
		V18	V19	V20	V21	V22	V23	V24	V25	V26	V27	V28	V29				
		w68	w72	w76	w80	w84	w88	w92	w96	w100	w104	w108	w120				
		±7	±7	±7	±7	±7	±7	±7	±7	±7	±7	±7	±7	±7	±7	±7	N/A
Local ECG	5.2.4					X									X		X
Serum chemistry ^d	5.2.5			X				X							X		
Hematology	5.2.5			X				X							X		
Urinalysis	5.2.5			X				X							X		
Urine pregnancy test (dipstick) ^e	5.2.5.1	X	X	X	X	X	X	X	X	X	X	X	X	X	X	X	
PK ^f	5.3.6			X				X							X		
ADA/nAb ^f	5.3.7.1			X				X							X		
ACQ-6	5.3.2.1		X			X							X		X		
AQLQ(S)+12	5.3.2.2		X			X							X		X		
WPAI+CIQ	5.3.2.3														X		
EQ-5D-5L	5.3.2.4	X	X	X	X	X	X	X	X	X	X	X	X	X	X	X	
Health care resource utilization	5.3.3	X	X	X	X	X	X	X	X	X	X	X	X	X	X	X	
Assessment of asthma exacerbations	5.1.1	X	X	X	X	X	X	X	X	X	X	X	X	X	X	X	X
Pre- BD spirometry	5.1.2				X								X		X		X
Post- BD spirometry	5.1.2														X		
Administration of IP ^{g,i}	6.8	X	X	X	X	X	X	X	X	X	X	X	X	X			

Table 2B Study Assessments Schedule – Adolescents: Weeks 68 to 120

Assessment/ activity	Refer to	Treatment											EOT	IPD ⁱ	FU	UNS ^h	
		V18	V19	V20	V21	V22	V23	V24	V25	V26	V27	V28					
		w68	w72	w76	w80	w84	w88	w92	w96	w100	w104	w108					
		Visit window (days) ^c															
		±7	±7	±7	±7	±7	±7	±7	±7	±7	±7	±7	±7	±7	±7	±7	N/A
Adverse events	7	X	X	X	X	X	X	X	X	X	X	X	X	X	X	X	X
Concomitant medication	3.5	X	X	X	X	X	X	X	X	X	X	X	X	X	X	X	X

^a Medical and asthma history, AEs and concomitant medications will be linked to the predecessor study to create a complete and continuous record for the patient.

^b Assessments done at the EOT visit of the predecessor study do not need to be repeated at Visit 1 of this study, as the data will be duplicated between study databases (see Section 4.1.1)

^c All visits are to be scheduled from the date of randomization but not from the date of previous visit

^d Detailed schedule for serum chemistry tests provided in Section 5.2.5, Table 3 and Table 4

^e For all adolescent females, urine HCG test to be done at center on each treatment visit before IP administration.

^f PK, ADA and nAb samples to be collected before IP administration.

^g In case of anaphylaxis additional samples to be taken (see Section 6.9)

^h Unscheduled visits may be initiated as needed, and additional assessments performed at these visits, at the discretion of the Investigator

ⁱ IPD visit should be completed within 4 weeks (+7 days) after last scheduled site visit

^j For adolescent patients in the EU, IP administration is Q8W with no injection of placebo at the 4 week interim visits.

D Days; EOT End-of-treatment; FU Follow-up; R Randomization; V Visit; UNS Unscheduled; W Week; IPD Premature IP Discontinuation

